6.2 Power and Sample Size Determination

SILK™ Analyses

Power estimates for SILK™ studies involving measurements of FSR of Aβ40 were determined by analysis of data provided by C2N, Inc., and modeled to evaluate a primary analytic goal of demonstrating a monotonic dose response relationship to Posiphen treatment.

Based on a two-sided t-test for the difference between two independent means at a significance level (alpha) of 0.05 and a statistical power of 80% (1-beta), a sample size of 5 subjects in each treatment group (n.active = 15) and 9 controls will provide at least 80% statistical power to detect a 27% change in the mean Aβ40 FSR. The following table provides estimated power analysis to detect different effect size reductions of FSR Aβ40 of 27% with 2-sided alpha and significance set at 0.05, assuming no dropouts during the SILK™ study:

Table 2. Estimated Power Analysis

	n.active= 12	n.active= 15	n.active= 18
n.cont= 8	0.783	0.822	0.848
n.cont= 9	0.812	0.851	0.876
n.cont= 10	0.836	0.874	0.898

This serves as justification for our sample size estimate of 24. We expect that if dropouts are to occur, they will occur before the SILK™ studies at day 23-25 and can be replaced to allow the full sample size of 24 for SILK™ being achieved.

6.3 Safety and Tolerability Analysis

Safety and tolerability will be assessed with physical examinations, vital signs, clinical laboratory values, use of concomitant medications, and AE reports. The frequencies of adverse events, serious adverse events and laboratory abnormalities between the participants across the three groups will be compared. The severity of cholinergic adverse events will be carefully evaluated taking the criteria in Appendix 5 into consideration (modified from Common Terminology Criteria for Adverse Events (CTCAE) version 4.03) as there is potential for an interaction between Posiphen and Donepezil through the inhibition of AChE, thereby resulting in increased cholinergic activity.

Each dose group will be completed and evaluated for safety and tolerability by the standing ADCS DSMB before the next dose group is initiated. Drug administration at the next higher dose level may not proceed until written confirmation is provided from the ADCS DSMB indicating that the results of the previous dose level were evaluated and that it is permissible to proceed to a higher dose level.

Subjects who do not tolerate study drug during the initial 3-week at-home treatment period will be discontinued and replaced by new subjects. If two subjects at a given dose are discontinued due to adverse events, no additional subjects will be added at this dose level until a safety review has been conducted. The ADCS DSMB will determine the appropriate dose level for additional subjects. The ADCS DSMB has the option to change the allocation of future patients to active drug versus placebo based on statistical advice to maintain an appropriate balance between placebo subjects and subjects on active drug.

6.4 PK Analysis

Plasma concentration-time data will be analyzed by non-compartmental methods using WinNonlin version 6.2.1 or greater. Calculations will be based on the actual sampling times recorded during the study. Only the subjects receiving Posiphen will be included in the PK analysis. From the plasma concentration-time data, the following PK parameters will be determined, as data permit: Area under the curve (AUC) τ , AUC $_{0-\infty}$, C_{max}, t_{max}, t $_{1/2}$, eff, V_{ss}, C τ , AR, and CL.

Dose-proportionality may be assessed on C_{max} and AUC τ as appropriate. Serial pre-dose trough concentrations C τ will be assessed for the attainment of steady-state.

The focus of the PK analysis will be to characterize the preliminary PK of Posiphen. Plasma concentration-time data for Posiphen will be listed and summarized descriptively (number of subjects (N), mean, median, standard deviation (SD), minimum (min), and maximum (max)) and graphically presented. PK parameters will be listed and summarized descriptively (N, mean, median, SD, min, max, and 95% CI) by each dose regimen. Also, a plasma/CSF comparison of the Posiphen PK will be conducted.

In addition, geometric means and between-subject coefficients of variation (CV) will be calculated for AUC τ , AUC $_{0-\infty}$, C_{max}, t_{max}, t $_{1/2}$, eff, V_{ss}, C τ , AR, and CL. All PK analyses will be performed by the ADCS Biomarker Core.

6.5 SILK™ Analysis

In SILK™ studies, the mass spectrometry data will be used to calculate the fraction of labeled A β for A β 38, 40, and 42 during 36 hours after administration of study drug for each subject, as described. The FSRs will be calculated by fitting a line to this data. FSRs for treated and untreated subjects will be compared by analysis of variance (ANOVA). The percentage of newly synthesized and degraded A β will be estimated over 36 hours by multiplying the mass spectrometry concentration of A β by the % of A β that contains ¹³C₆-leucine at each time point. This will be used to estimate the AUC of the drug for decreasing the amount of newly produced A β ([Bateman 2009](#)).

6.6 Criteria for the termination of the trial

The trial may be terminated by the Project Directors and/or Annovis Bio, Inc., based on issues of safety, feasibility, and Data Safety Monitoring Board (DSMB) recommendations.

7 STUDY DRUG AND CONCOMITANT MEDICATIONS

7.1 Name and Description of IP and Comparator

Posiphen will be prepared in 60 mg gelatin capsules, without excipients or fillers. Matching placebo capsules (non-lactose compound) will be prepared with an inert inactive excipient generally recognized as safe for human pharmaceutical use. Annovis Bio, Inc.'s vendor, Frontage Laboratories, will provide both study drug and placebo.

7.2 Dosage

The study drug is to be taken orally; one capsule, up to three times per day depending on treatment group (one in the morning, one in the middle of the day, and one in evening/bed time), with or without food, for 21-23 days at home (depending on when the confinement visit is scheduled). An additional 2 days of drug will be administered during the confinement visit for a total 23-25 days of Posiphen exposure. The study drug will be size 5, hard gelatin capsules. The following table describes the number and type of capsules to be taken each day based on treatment group. The quantity of 60 mg Posiphen capsules and placebo capsules to be taken each day will depend on the assigned treatment group:

Table 3. Quantity of Capsules per Day

Treatment Group	Quantity of Capsules per day	
	60 mg Posiphen	Matching Placebo
Posiphen 60 mg Treatment Group	1	2
Posiphen 120 mg Treatment Group	2	1
Posiphen 180 mg Treatment Group	3	0
Placebo	0	3

Based on when the confinement visit is scheduled, participants will take 21-23 days of the drug at home. Participants must take 80% of all doses (across 21-23 days), and should take at least 80% of all doses in the last week before the confinement visit. Blister packs will be examined in clinic at the pre-confinement visit to assess compliance overall and in the last week.

7.3 Packaging/Dispensing/Labeling

Frontage Laboratories will prepare the study drug (Posiphen capsules and placebo capsules) to preserve the blind, i.e., identical color and shape opaque hard gelatin capsule shells. The study drug (Posiphen) and placebo capsules will be packaged in identical blister packs with labels including the requisite cautionary statement "CAUTION: Limited by Federal (United States) Law to Investigational Use Only".

In order to preserve the blind, Frontage Laboratories will provide the initial drug supply and subsequent resupply to the sites to dispense to participants.

The dosing schedule and storage requirements will be clearly explained to the participants and caregiver before dispensing the study drug, and it will be printed on the labels.

All clinical trial material dispensed under this protocol will bear the requisite cautionary statement "CAUTION: Limited by Federal (United States) Law to Investigational Use Only".

7.4 Storage

Both Posiphen capsules and the matching placebo capsules (non-lactose compound) must be stored at room temperature (15-30 °C; 59-86 °F), protected from moisture, in a locked area with limited staff access.

7.5 Drug Accountability

The investigator is responsible for investigational product reconciliation and records maintenance. In accordance with all applicable regulatory requirements, the investigator or designated site staff must maintain investigational product accountability records throughout the course of the study. The responsible person(s) will document the amount of investigational product dispensed to and returned by subjects. All used and unused study drug containers must be returned to the site for accountability. Once authorized by a clinical monitor, unused study drug (including partially used blister packs) may be destroyed on site per appropriate site SOPS or should be shipped back to Anovis Bio, Inc. for destruction.

7.6 Compliance

Site personnel will assess compliance based on the amount of study drug dispensed to and returned by the participants, together with any related information, including the administration of study drug by study staff during the confinement visit. Participants must take 80% of all doses at home (21-23 days) depending on the confinement visit date and should take at least 80% of all doses in the last week prior to the confinement visit. Site personnel will count capsules and evaluate compliance from the blister packs at the pre-confinement visit.

Prior to the pre-confinement visit, site personnel will also contact the participant and study partner to remind them of the dose regimen, in particular to ensure that the necessary level of compliance has been achieved to continue with the confinement visit procedures.

Site personnel will assess compliance at the pre-confinement visit and again at the time of admission for the confinement visit. If participants are found to be < 80% compliant for all doses at home and in the last week there is an insufficient level of compliance, the site must consult with the Project Directors (and/or Medical Monitor) regarding timing and conduct of the confinement visit procedures. It is possible that subjects will be discontinued early from the study due to insufficient drug compliance.

During the leucine infusion, participants must comply with a low leucine diet – 1500 mg or less of leucine per day. The kitchen on-site will have the responsibility of preparing low leucine meals meals/snacks and maintaining a food journal for each individual. (Refer to Appendix 4 for a sample low leucine menu).

7.7 Breaking the Blind

Only in the case of an emergency, when knowledge of whether the participant has received the investigational product is essential for the clinical management or welfare of the participant, may the investigator request to unblind a participant's treatment assignment. If the investigator needs the blind to be unmasked for a subject for any reason, the investigator must contact the Medical Monitor (and/or Project Directors) to obtain an approval. The blind will need to be broken centrally at the ADCS Coordinating Center. If the blind is broken, whether it be by accident or for the welfare of the participant, the investigator MUST contact the Medical Monitor. Refer to the study procedures manual for detailed procedures related to breaking the blind and reporting.

7.8 Overdose

No specific antidote for the overdose of Posiphen is known; however, signs or symptoms of possible overdose should be noted and treated. The Medical Monitor and Project Directors should be notified as well. Because strategies for the management of overdose are continually evolving, it is advisable to contact a poison control center to determine the latest recommendations for the management of an overdose of any drug. Although Posiphen is a weak AChE inhibitor, based upon overdose information published in prescribing information for related products, overdose with AChE inhibitors can result in cholinergic crisis characterized by severe nausea, vomiting, salivation, sweating, bradycardia, hypotension, respiratory depression, collapse and convulsions. Increasing muscle weakness is a possibility and may result in death if respiratory muscles are involved. Tertiary anti-cholinergics such as atropine may be used as an antidote for overdosage. Intravenous atropine sulfate titrated to effect is recommended. Atypical responses in blood pressure (BP) and HR have been reported with other cholinomimetics when co-administered with quaternary anticholinergics such as glycopyrrolate. It is not known whether dialysis (hemodialysis, peritoneal dialysis, or hemofiltration) is an effective treatment for overdose.

7.9 Concomitant Medications

7.9.1 Prohibited Concomitant Medications

Current use of anti-coagulants (e.g., warfarin (Coumadin), dabigatran (Pradaxa) or anti-platelet drugs (e.g., aspirin, Plavix)), other than aspirin up to a dose of 325 mg per day, is prohibited. Prospective subjects who can safely discontinue these medications for 4 weeks before screening and remain off these medications throughout the study, can be considered for inclusion in the study.

Use of the following medications is prohibited within 4 weeks of screening and throughout the study except as noted in Section 7.9.2:

- specific psychoactive medications (tricyclic antidepressants, antipsychotics (except ≤ 50 mg quetiapine daily, risperidone ≤ 1.5 mg/day, olanzapine ≤ 5 mg/day, and aripiprazole ≤ 10 mg/day)
- mood-stabilizing psychotropic agents (e.g., lithium salts)
- psychostimulants
- opiate analgesics
- antiparkinsonian medications

- anticonvulsant medications
- systemic corticosteroids
- CNS active antihistamines for allergy or sleep (daily use)

Investigational agents are prohibited 4 weeks prior to entry and for the duration of the trial. Also, exclusionary, is previous treatment with an investigational small molecule with anti-amyloid properties or passive immunization against A β within 1 year of entry or previous treatment with an active immunization against amyloid. This will also include AduhelmTM, an A β -directed monoclonal antibody that received accelerated FDA approval for treatment of early AD but which is prohibited in this study.

Initiation of prohibited medications during the course of the study is discouraged, however, if an excluded medication is initiated after screening, the site should consult with the Project Directors and Medical Monitor for further guidance.

7.9.2 Permitted Concomitant Medications

This protocol allows concomitant treatment with cholinesterase inhibitors and/or memantine if on a stable dose (FDA approved drug ranges) for 12 weeks prior to screening. However, participants are only permitted to be on a maximum of 10 mg/day of Aricept (donezepil).

Initiation of or modifications to concomitant AD medications during the course of the study is discouraged; however, if a change occurs or a new medication is initiated, the site should consult with the Project Directors and Medical Monitor for further guidance. The addition of Aduhelm is not permitted during the trial.

Gabapentin and pregabalin for non-seizure indications, stable doses of bladder medication, and non-opiate analgesics for pain management are permitted.

Use of benzodiazepines for treatment on an as-needed basis for insomnia or daily dosing as anxiolytics is permitted. If they are being given chronically, use of sedatives or hypnotics should be avoided for 8 hours before administration of cognitive tests. If sedating medication is given for any short-term use, then all cognitive assessments must be administered at least 24 hours after administration of the sedative. Sedating medication should not be taken the night before the baseline visit, the day of the baseline visit, the night before the pre-confinement visit, or the day of the pre-confinement visit.

8 STUDY POPULATION

Up to 24 participants with early AD including those with a clinical profile consistent with MCI or mild AD will be enrolled in this study, in accordance with the criteria specified below. Subjects who do not meet all inclusion criteria, disease diagnostic criteria, or who meet any exclusion criteria may not be randomized into the study without prior approval from the Project Directors and Medical Monitor.

8.1 Inclusion Criteria

Subjects must meet the following criteria:

1. Male or female aged 55 to 89 years (inclusive), in good health, no frailty.

2. Female participants must be post-menopausal for at least 2 consecutive years or surgically sterile (bilateral tubal ligation, hysterectomy or bilateral oophorectomy) for at least 6 months prior to screening.
3. Female participants will be given a urine pregnancy test at the screening visit for which they should test negative.
4. Clinical profile consistent with MCI or mild AD, consistent with the core clinical criteria outlined in the NIA-AA Guidelines (2011).
5. MMSE score between 17 and 30 (inclusive).
6. CDR global score of 0.5 with a memory score of 0.5 or greater, or CDR global score of 1.0.
7. Participant likely to tolerate all study procedures per PI judgment.
8. To qualify for entry, subjects will have a CSF A β 42/ A β 40 ratio below 0.131 that is consistent with Alzheimer's disease as measured via mass spectrometry by C2N.
9. General cognition and functional performance sufficiently preserved that the subject can provide written informed consent.
10. A minimum of 6 years of education or good work history.
11. Study partner is available who has frequent contact with the subject (e.g., average of 10 hours per week or more), and can accompany the subject to most visits to answer questions about the subject. The study partner is required to attend the entire screening visit and the baseline visit. The study drug is dispensed to the participant at the baseline visit and the study partner (or other individual) should also oversee study drug administration if needed to ensure compliance with dose regimen. At a minimum, the study partner should stay for the first 3 hours of the confinement visit and return at the discharge to drive the subject home.
12. No evidence of current suicidal ideation or previous suicide attempt in the past month as evaluated in the Columbia Suicide Severity Rating Scale.
13. MRI scan within the 12 months prior to screening without evidence of infection, infarction, or other focal lesions and without clinical symptoms suggestive of intervening neurological disease. Lacunes that are not believed to contribute to the subject's cognitive impairment are permissible. If there is no MRI available within a 12-month timeframe, then an MRI must be performed as part of the screening procedures for eligibility.
14. Stability of permitted medications for 4 weeks prior to baseline. NOTE: Cholinesterase inhibitors and or memantine are allowable only if stable for 12 weeks prior to screen. If taking Arciept (donezepil), no more than 10 mg/day is permitted during the course of the study.
15. Adequate visual and hearing ability (physical ability to perform all the study assessments).
16. Good general health with no disease expected to interfere with the study. Subjects may have common age-related disorders (i.e., hypertension, type II diabetes, dyslipidemia, and hypothyroidism) as long as these disorders are being controlled by diet or medication.
17. Must speak English, Spanish, or Korean fluently.

8.2 Exclusion Criteria

Subjects meeting any of the following criteria must not be included in the study:

1. Has a history of a psychiatric disorder such as schizophrenia, bipolar disorder or major depression according to the criteria of the most current version of the Diagnostic and Statistical Manual of Mental Disorders (DSM). Mild depression or history of depression that is stable on treatment with a tricyclic antidepressant SSRI or SNRI medication at a stable dose is acceptable.
2. Other neurodegenerative diseases, including Parkinson's disease and Huntington's disease, or cerebral tumor.
3. Dementia other than AD, such as Acquired Immunodeficiency Syndrome (AIDS), Creutzfeldt-Jakob disease (CJD), Lewy Bodies dementia (LBD), Cerebrovascular dementia (CVD), Progressive Supranuclear Palsy (PSP), or normal pressure hydrocephalus (NPH).
4. History of a seizure disorder.
5. Clinically significant abnormalities in screening laboratory or ECG results.
6. Has current serious or unstable illness including cardiovascular, hepatic, renal, gastroenterologic, respiratory, endocrinologic, neurologic, psychiatric, immunologic, or hematologic disease or other conditions that, in the investigator's opinion, makes them ineligible for participation in this study.
7. Has four or more microinfarcts as noted in the MRI scan.
8. Has cancer or has had a malignant tumor within the past 3 years, except patients who underwent potentially curative therapy with no evidence of recurrence. (Patients with stable untreated prostate cancer or skin cancers are not excluded).
9. According to the criteria of the most current version of the DSM, alcohol abuse, alcohol dependence, or drug abuse in the past 5 years.
10. Participation in another clinical trial with an investigational agent and have taken at least one dose of study medication, unless unblinded on placebo, within 16 weeks prior to screening. (The end of a previous investigational trial is the date the last dose of an investigational agent was taken).
11. Resides in a skilled nursing facility.
12. Subjects with infection or inflammation of the skin or skin disease at or in proximity to the lumbar puncture site.
13. History of lumbar spine surgery or chronic low back pain (CLBP).
14. Subjects whom the site PI deems to be otherwise ineligible.
15. Has a deep brain stimulator (DBS).

9 DESCRIPTION OF STUDY VISITS

Each subject will have a 42 day screening period followed by approximately 21-23 days of treatment at home. The study visits are described below and outlined in the Schedule of Events in Appendix 1 as well as in the Study Schematic Diagram in Appendix 2.

9.1 Pre-screening

During the prescreen phase, sites will identify potential participants through a variety of mechanisms (i.e., reviewing participants enrolled in ADRC centers, de novo recruitment, and referrals) and assess if they may potentially qualify for the study following the site's standard practice.

9.2 Screening Visit

The screening visit should occur up to 42 days before the baseline visit. The screening visit procedures may be completed over multiple days and will typically require at least two in-clinic visits, one of which will be to perform the lumbar puncture.

Potential participants, or legally authorized representatives, and their study partners must sign an informed consent form prior to administration of any study-related procedures. Information regarding the subject's demographics, concurrent medications, and medical history will be collected along with cognitive assessments, physical examination, and neurological examination.

Safety assessments will include an ECG and MRI scan that will need to be read locally and reviewed by the site investigator to confirm eligibility. The clinical safety laboratory blood and urine tests will be sent to a central lab for analysis. The screening safety laboratory tests will be comprised of a metabolic panel, complete blood count, coagulation panel, and urinalysis as listed in Section 12.1.3. Coagulation panel results must be obtained prior to performing the lumbar puncture. The urinalysis will include a pregnancy test for female participants.

A lumbar puncture will be performed as part of the screening visit, in the morning (before 10 am is recommended), after an overnight fast. 16-20 mL CSF will be typically obtained. 2 mL CSF will be sent for analysis by the site (total protein, glucose, cell count) to their local lab and the remainder will be shipped to the ADCS Biomarker Core. The CSF sent to the ADCS Biomarker Core should be placed into a 14 ml conical polypropylene tube, inverted gently 3-4 times, then centrifuged at 1500 x g for 10 minutes at room temperature. Next, the supernatant should be aliquoted into 2.0 ml tubes, frozen at -80°C, and shipped overnight to the ADCS Biomarker core. If CSF cannot be shipped on the day of draw, it will be frozen and stored at -80 °C by the site until it can be shipped on dry ice. The ADCS Biomarker Core will send CSF samples to C2N and C2N will analyze the screening CSF for Aβ42/ Aβ40 levels. All LP supplies will be provided to sites by ADCS.

Blood will be drawn at the time of the LP for research procedures. This will consist of 3 mL of plasma, and 10 mL of blood for APOE genotyping and storage of DNA. Blood samples should be shipped overnight at ambient temperature to the ADCS Biomarker Core. For a complete list of procedures, refer to the Schedule of Events (Appendix 1).

Cognitive assessments must be done either prior to the lumbar puncture or within 48 hours after the lumbar puncture. Cognitive assessments should not be administered when the subject is in

a fasted state. Given the timing of the MRI and the LP, during the screening visit the cognitive testing can be scheduled up to 7 weekdays prior to the LP visit date.

Once all screening visit procedures are completed, all information related to eligibility, including screening lab results, must be reviewed by the site investigator to assess the subject's eligibility before proceeding to the baseline visit.

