5.3 Risk/Benefit Associated with SILK™ Procedure and CSF Sampling

The most frequent adverse event associated with these studies was post-lumbar puncture headache. This was successfully managed by blood patching if a participant is unresponsive to orally administered fluids and/or caffeine.

Other potential risks include meningitis, pain or tingling sensation in the lower extremities, temporary eye weakness or double vision, infection or bleeding at the site of catheter insertion, pain at the site of insertion, backache, epidural or subdural bleeding, infection, paralysis and potential injury to the nerve root.

In studies conducted at C2N Diagnostics and at Washington University, the rate of post-lumbar puncture headache requiring a blood patch is about 10% in older individuals ([name], personal communication).

5.4 Risk/Benefit Associated with Investigational Drugs Intended to Reduce β -amyloid in the Brain

In 2010, Food and Drug Administration (FDA) sent a notice to all sponsors of investigational compounds that are intended to treat Alzheimer's disease by reducing A β in the brain of the occurrence of imaging abnormalities believed to represent cerebral vasogenic edema. These imaging abnormalities were noted in a study of a monoclonal antibody (Salloway, 2013) and were, in the majority of instances, asymptomatic, and their presence was detected by routine brain magnetic resonance imaging (MRI). Symptoms, when present in association with such imaging abnormalities, were reported to include headache, worsening cognitive function, alteration of consciousness, seizures, unsteadiness, and vomiting. In most instances, the occurrence of such imaging abnormalities, even when symptomatic, did not require treatment beyond discontinuation of the investigational compound, with imaging abnormalities then resolving. Infrequently, high-dose steroid therapy was administered in the presence of prominent symptoms.

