12.2 Biofluids

12.2.1 CSF for Biomarkers

Standard Lumbar Puncture:

A lumbar puncture will be performed as part of the screening visit, in the morning (before 10am is recommended), after an overnight fast. 2ml CSF will be sent for analysis by the site (total protein, glucose, cell count) to a local lab. The remaining CSF will be placed into a 14 ml conical polypropylene tube, inverted gently 3-4 times, then centrifuged at 1500 x g for 10 minutes at room temperature. The supernatant should be aliquoted into 2.0 ml tubes, frozen at -80°, and shipped overnight to the ADCS Biomarker Core. The ADCS Biomarker Core will subsequently send these samples to C2N for processing and analysis according to Biomarker core SOPs. Analyses will include AD biomarkers (e.g., A β , sAPPs, tau).

CSF samples will be banked in the biospecimen repository of the ADCS Biomarker Core for various future research studies; access to samples will be granted according to SOPs established by ADCS Biomarker Core.

Prior to the LP, a coagulation panel will be obtained to rule out a clotting disorder. Participants taking an anti-platelet agent (e.g., Plavix) must be discontinued from that agent for a minimum of 5 days prior to the lumbar puncture. These participants may continue with the agent after a minimum of 24 hours post LP. Participants who are taking anticoagulants (e.g., warfarin (Coumadin) and/or dabigatran (Pradaxa) may not undergo an LP and are not suitable to participate in this study.

When done at the same visit, the LP should occur after the MRI scan. When done at the same visit, if the MRI scan can only be scheduled prior to the LP, the site must contact ADCS Clinical Operations for permission before proceeding. In the unplanned event that the MRI does not precede the LP, there should be a minimum window of 72 hours between the MRI and the LP. LP under fluoroscopy is permitted; however, the site must contact ADCS Clinical Operations for permission before proceeding. Site personnel should advise the subject that use of fluoroscopy (x-rays) involves exposure to radiation.

Each study participant or a person designated to speak for them will be contacted by phone approximately 24 hours after the LP to confirm participant well-being and any adverse events.

CSF Sampling:

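### Section 9.2 lets screening cognitive tests follow the lumbar puncture, so people who fail MMSE or CDR can be punctured first and the only pre-drug MMSE can be a post-puncture score

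*Protocol*

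**What the plan says.** Protocol Section 9.2 gives two permitted positions for the screening cognitive tests: "Cognitive assessments must be done either prior to the lumbar puncture or within 48 hours after the lumbar puncture". It then adds an option, not a duty, to test earlier: "cognitive testing can be scheduled up to 7 weekdays prior to the LP visit date".

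Two other rules in the same section bear on the order. The LP is done "in the morning (before 10 am is recommended), after an overnight fast". The sentence beginning "Cognitive assessments should not be administered when the subject is in" ends by naming the fasted state.

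The only result that Section 9.2 requires before the LP is the coagulation panel. The investigator's eligibility review comes once all screening procedures are complete and before the baseline visit. Section 8.1 makes MMSE (17 to 30) and CDR entry criteria.

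Appendix 1 places MMSE at Screening and Pre-confinement only. Section 9.3 mentions cognitive assessments at baseline, but the schedule lists ADAS-Cog12 and NPI there, not MMSE. SAP 5.2.2 and 5.2.3 adjust for baseline MMSE, and 5.2.3 also compares mean change in MMSE between active and placebo.

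On the hazard, Protocol Section 5.3 says: "The most frequent adverse event associated with these studies was post-lumbar puncture headache".

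**The concern.** Two things are at stake.

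The first is participant burden. MMSE and CDR need only an interview. If they may follow the LP, someone who was never going to qualify can have 16-20 mL of CSF withdrawn before anyone finds out.

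The second is the quality of a baseline value that has no backup. No MMSE is taken at the baseline visit, so a screening score obtained within two days after an LP is the entry score, the reference for the Aim 6 MMSE change and the model covariate. The later MMSE, at Pre-confinement, comes 1-3 days before admission and so before the catheter. The two scores may then be taken under different conditions.

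**Working it through.** The plan states no figure on this point, so the check is mainly a reading of the passages side by side.

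**1. Order of events that the text permits**

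| Item | Must precede the screening LP? | Source |
|---|---|---|
| Coagulation result | Yes | Protocol 9.2, 12.2.1 |
| MMSE, CDR | No | Protocol 9.2 |
| Check against entry criteria | No; after all screening procedures | Protocol 9.2 |

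Consent, coagulation result, fasted LP, then MMSE and CDR within 48 hours, then screen failure is thus a compliant sequence. Because the LP is fasted and testing while fasted is barred, tests done on the LP day will tend to fall after it. Section 11.1 is headed as covering both cognitive and clinical evaluations, so CDR may not count as a cognitive assessment. In that case Section 9.2 sets no timing for CDR relative to the LP, and CDR can still come second.

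**2. Avoidable LPs**

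Let s be the share of screening LPs done before MMSE and CDR, and f the share of those people who then fail MMSE or CDR. Avoidable LPs per 100 = 100 × s × f. The documents give neither value. Assuming f = 10% to 30% and s = 1, the result is 10 to 30 per 100; it falls in proportion to s and is zero where sites always test first. This shows how the count scales and is not an estimate.

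**3. Direction of an eligibility error**

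Section 11.1.4 gives the MMSE range as 0 to 30, so the upper entry limit is the scale maximum and the criterion can fail only on a low score. A temporarily lowered MMSE can therefore wrongly exclude a person already punctured, but cannot wrongly admit one. Section 9.2.2 normally allows one re-screen, typically at least 3 months later.

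**4. Effect on the active-placebo comparison of MMSE change**

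Inputs: 3 cohorts of 5 active and 3 placebo (Protocol 6), so 15 active and 9 placebo; an assumed dip of 3 points at screening in one participant, gone by Pre-confinement.

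- If that person is on active, the active mean change rises by 3/15 = 0.20.
- If on placebo, the placebo mean change rises by 3/9 = 0.33, so the active-minus-placebo difference falls by 0.33.
- Chance of active = 15/24 = 0.625; of placebo = 9/24 = 0.375.
- Expected shift in the difference = 0.625 × 0.20 − 0.375 × 0.333 = 0.125 − 0.125 = 0.
- Standard deviation of that shift = √(0.625 × 0.20² + 0.375 × 0.333²) = √(0.0250 + 0.0417) = 0.26.

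For a 1-point dip the shifts are 1/15 = 0.07 and 1/9 = 0.11. These are unadjusted values. Adjusting for baseline MMSE, as SAP 5.2.3 plans, would absorb part of them.

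**5. The LP exception**

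Section 9.2.1 accepts an LP done for another study up to 90 days before baseline, while screening runs up to 42 days before baseline. An LP at day −90 and tests at day −42 are 90 − 42 = 48 days apart. Those tests are neither before the LP nor within 48 hours after it, so the present rule does not fit this case.

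**6. MRI and LP order (separate minor point)**

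Section 12.2.1 says that at a shared visit the LP should come after the MRI. The next sentence, also about a shared visit, reads: "if the MRI scan can only be scheduled prior to the LP, the site must contact ADCS Clinical Operations". It requires permission for the very order that the preceding sentence asks for.

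**The case against.** The strongest reply is that this is a permissive window that sites would seldom use badly. Screening typically takes at least two clinic visits, one of them for the LP. The coagulation result must be back before the LP, so an earlier, non-fasted contact usually exists and is the natural time for an interview. Sites also pre-screen. All of this is fair, and it limits how often the problem would arise. It does not close the gap, since no sentence requires the tests or the check to come first.

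A reader might go further and infer that a low post-LP baseline would make Posiphen look beneficial. The documents do not support that. The screening MMSE precedes randomization, the trial is blinded and placebo-controlled, and a dip falls on either arm by chance; in a placebo participant it works against the drug.

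A reader might also take the 48 hours to be a stated headache period. The protocol gives no onset or duration for post-LP headache and no effect of an LP on MMSE. Its headache statement, and the figure of about 10% needing a blood patch, stand under the heading for SILK and CSF sampling and are not shown to apply to a single screening LP. The call about 24 hours after the LP asks about well-being and adverse events in general. Overlap with headache is a reasonable inference and no more.

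The reach is also limited. ADAS-Cog12 and NPI have their own baseline-visit values, Aim 6 is secondary, and the primary FSR model adjusts for age and gender, not MMSE. Logical Memory is neither an entry criterion nor an Aim 6 outcome.

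**Conclusion.** The point holds as a matter of text. Section 9.2 allows a person who will fail MMSE or CDR to be punctured first, and it allows the only pre-drug MMSE to be a post-LP score. The burden argument needs no assumption about headache or bias: an interview that can exclude someone should come before an invasive procedure.

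The statistical consequence is smaller. It is avoidable noise and possible chance imbalance in one secondary measure and one covariate, with an expected shift of zero in the active-placebo contrast. The 0.20 and 0.33 point shifts rest on an assumed 3-point dip in one participant. The 10 to 30 avoidable LPs per 100 rest on an assumed failure rate and on all such people being tested after the LP. The documents supply none of these rates. The change is worth making because it is nearly free, not because the trial's main conclusions depend on it.

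**What to change.** - In Section 9.2, for participants who have a screening LP for this study, remove the post-LP alternative. Require MMSE and CDR to be completed and checked against the entry criteria before the LP, using the existing allowance of up to 7 weekdays beforehand.
- State separately how the timing of these tests works when an earlier LP is accepted under Section 9.2.1.
- As a separate edit, reconcile the two same-visit MRI and LP sentences in Section 12.2.1.

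The cost is wording, with the same tests and staff. The downside is that a site may occasionally have to move the cognitive session earlier.
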